3.3 Data Collection and Statistical Considerations

Data collection is summarized in Table 1. Body temperature and pulse oximetry will be checked by the inpatient nursing staff at least three times daily, beginning with randomization and ending with resolution of fever and hypoxemia, respectively, or study completion. Body temperature and pulse oximetry orders will be entered into the electronic medical record by a member of the research staff if not already ordered as part of standard of care. Documentation will be entered into the electronic medical record in the form of a research progress note informing the treating physician of vital signs ordered for research purposes to avoid duplication of tasks. The visual analog scale (VAS) for pain will be assessed once daily beginning with randomization and ending with resolution of moderate to severe pain or study completion. Laboratory evaluation will include a complete blood count (white blood cell count, hemoglobin and hematocrit, and platelet count). Complete blood count (white blood cell count) will be obtained daily beginning with randomization and ending with resolution of leukocytosis or study completion. Complete blood count (hemoglobin, hematocrit, and platelet count) will be obtained daily beginning with randomization and ending with study completion in subjects receiving UFH. Anti-Xa UFH level will be ordered according to the heparin infusion protocol as detailed earlier in subjects receiving UFH. Complete blood count will be entered into the electronic medical record by a member of the research staff if not already ordered as part of standard of care. Documentation will be entered into the electronic medical record in the form of a research progress note informing the treating physician of laboratory studies ordered for research purposes to avoid repeat blood draws. All blood samples will be collected by the inpatient phlebotomy team or nursing staff and sent to the inpatient laboratory for analysis.

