The primary clinical outcome is duration of hospitalization. Secondary clinical outcomes include the duration of hypoxemia, duration of fever, duration of leukocytosis, duration of moderate to severe pain, total dose of opioids, and the number of red blood cell transfusions administered. Additional clinical outcomes will include the rate of transfer to the ICU, requirement for mechanical ventilation, and development of MODS.

Duration of hospitalization will be defined as beginning with randomization and measured in hours. Conclusion of hospitalization will be defined as the time of order entry into the inpatient electronic medical record system stating the patient is appropriate for medical discharge, per the discretion of the treating physician. Duration of hypoxemia will be defined as beginning with randomization and measured in hours. Hypoxemia will be defined as arterial oxygen saturation less than 90% according to pulse oximetry and/or the continued need for supplemental oxygen. If the patient's baseline arterial oxygen saturation is less than 90%, hypoxemia will be defined as a decrease in arterial oxygen saturation below the patient's baseline. Similarly, if

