the patient has a baseline supplemental oxygen requirement, hypoxemia will be defined as an increase in supplemental oxygen requirement above the patient's baseline. If the patient does not meet criteria for hypoxemia following the initial 3 nursing vital signs assessments after randomization, hypoxemia will be considered absent and no further assessments will occur. Resolution of hypoxemia will be defined as failure to meet the criteria for hypoxemia on 3 consecutive nursing vital signs assessments. Duration of fever will be defined as beginning with randomization and measured in hours. Fever will be defined as a body temperature greater than or equal to 38.0 degrees Celsius measured by a thermometer orally. If the patient does not meet criteria for fever following the initial 3 nursing vital signs assessments after randomization, fever will be considered absent and no further assessments will occur. Resolution of fever will be defined as failure to meet the criteria for fever on 3 consecutive nursing vital signs assessments. Duration of leukocytosis will be defined as beginning with randomization and measured in hours. Leukocytosis will be defined as a white blood cell count greater than 10,000 per liter. If the patient does not meet criteria for leukocytosis following the initial 2 complete blood counts after randomization, leukocytosis will be considered absent and no further assessments will occur. Resolution of leukocytosis will be defined as failure to meet the criteria for leukocytosis on 2 consecutive complete blood counts. Duration of moderate to severe pain will be defined as beginning with randomization and measured in hours. If the patient does not report a score of 4 or greater on the VAS for pain following the initial 2 assessments after randomization, moderate to severe pain will be considered absent and no further assessments will occur. The end of the duration of moderate to severe pain will be defined as 2 consecutive scores of less than 4 on the VAS for pain. Total dose of opioids will be defined as beginning with randomization, ending with study completion, and measured in milligrams of oral morphine equivalents. Red blood cell transfusions will be given routinely as standard clinical practice in acute chest syndrome with the goal of preventing progression to acute respiratory failure. Number of red blood cells transfused will be defined as beginning with randomization, ending with study completion, and measured in units of packed red blood cells received. Red blood cell transfusions given for suspected or proven hemorrhage secondary to UFH will not be included in the outcome as defined above. Rate of transfer to the ICU, requirement for mechanical ventilation, and development of MODS will be defined as beginning with randomization, ending with study completion, and categorized as present or absent. Further, MODS will be defined as the acute development of 2 or more organs or organ systems unable to maintain homeostasis in a critically ill individual.

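### Leukocytosis is judged against one fixed white-count cut-off with no patient-baseline rule, so a patient whose usual count lies above it may stay unresolved after recovery

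*Combined protocol and SAP*

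**What the plan says.** All the definitions are in section 3.3.

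- **Hypoxemia** has two baseline clauses. If usual saturation is under 90%, "hypoxemia will be defined as a decrease in arterial oxygen saturation below the patient's baseline". If the patient already uses oxygen, "hypoxemia will be defined as an increase in supplemental oxygen requirement above the patient's baseline".
- **Leukocytosis** has none. "Leukocytosis will be defined as a white blood cell count greater than 10,000 per liter". It counts as absent if the first two counts after randomization do not exceed the cut-off. Otherwise it ends by this rule: "Resolution of leukocytosis will be defined as failure to meet the criteria for leukocytosis on 2 consecutive complete blood counts".
- **Measurement**: "Complete blood count (white blood cell count) will be obtained daily beginning with randomization and ending with resolution of leukocytosis or study completion". Table 1 runs from Day 1 to Day 7.
- **Pain** also has a fixed threshold: the end of moderate to severe pain "will be defined as 2 consecutive scores of less than 4 on the VAS for pain".

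The history items in section 3.3 and the Table 1 footnotes include hydroxyurea use and chronic lung disease (the latter defined by baseline saturation or home oxygen). They include neither a usual white count nor a usual pain score. The analysis is descriptive, and section 3.3 wants effect and variance estimates for sizing a later trial.

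**The concern.** The hypoxemia clauses accept that a chronically abnormal value is not part of the acute episode. The leukocytosis definition does not apply that reasoning. A patient whose usual count is above the cut-off is likely to be classed as having leukocytosis at entry, and may still be classed that way once the episode is over.

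For such a patient the duration tends to measure time under observation, not recovery. Chance differences between arms of 10 in usual white count could then look like a treatment difference, and the spread passed on to the next trial would be a mixture of two quantities. Because the usual count is not collected, the planned data cannot repair this afterwards.

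**Working it through.** The plan states no figure that depends on this definition, and the sample size of 20 is expressly non-statistical, so there is nothing to reproduce. The steps below are illustrations on stated assumptions.

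**Inputs from the documents.** Cut-off 10,000; two consecutive counts; daily counts, so at most about 7 in the Table 1 window; 20 patients, 10 per arm. The printed unit is per liter, and 10,000 / 1,000,000 = 0.01 per microliter, which is implausible. I read it as per microliter. The unit is a separate correction, and this point remains after it.

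**Inputs assumed.** Steady-state mean 9 to 12 and SD 2.5 to 3.5 thousand per microliter between patients; day-to-day coefficient of variation (CV) 10% to 20% within a patient; normal and independent daily values.

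**1. Share with a usual count above the cut-off.** P = 1 − Φ((10 − mean)/SD).
- Mean 9: SD 2.5 gives 1 − Φ(0.40) = 0.345; SD 3.5 gives 1 − Φ(0.286) = 0.388.
- Mean 12: SD 2.5 gives 1 − Φ(−0.80) = 0.788; SD 3.5 gives 1 − Φ(−0.571) = 0.716.
- Range 34% to 79%, or 6.9 to 15.8 of 20.

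**2. Chance that a patient already back at the usual level meets the rule.** Let r be the usual count divided by the cut-off. One day's count is at or below the cut-off with probability p = Φ((1 − r)/(r × CV)). To get the chance of at least one run of two in 7 days, let a and b be the probabilities of no run so far with the last count above, or not above, the cut-off. Start at a = 1, b = 0, and each day replace (a, b) by ((a + b)(1 − p), a × p). The answer is 1 − a − b after 7 days.
- r = 0.9: 95% to 99.6%
- r = 1.1: p = 0.18 to 0.32, giving 16% to 42%
- r = 1.2: p = 0.05 to 0.20, giving 1% to 20%
- r = 1.3: p = 0.01 to 0.12, giving 0.1% to 8%
- r = 1.5: p = 0.0004 to 0.05, giving 0% to 1%

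**3. Both together.** Averaging the chance of not resolving over the part of each step 1 distribution above 10 gives about 4.5 of 20 (mean 9, SD 2.5, CV 20%) to 14.5 of 20 (mean 12, SD 2.5, CV 10%). This is fewer than in step 1, because some patients just above the cut-off do meet the rule.

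**4. Effect on the summary.** Assume an unresolved patient is entered at 7 × 24 = 168 hours and others resolve at 48 to 96 hours. One extra unresolved patient in an arm of 10 moves that arm's mean by (168 − 96)/10 = 7.2 to (168 − 48)/10 = 12 hours. If resolvers have mean 72 and SD 36 hours and 30% are unresolved, the mean is 0.7 × 72 + 0.3 × 168 = 100.8. The variance is 0.7 × (36² + 72²) + 0.3 × 168² − 100.8² = 2,842.6, so the SD is 53.3 instead of 36.

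**5. Would a bare return-to-baseline rule do?** No. A recovered patient is at or below the baseline on about half of days. With p = 0.5, 34 of the 2⁷ = 128 possible sequences contain no run of two, so 34/128 = 27% would still be unresolved. A margin of one within-patient SD gives p = Φ(1) = 0.841, and step 2 then gives 99%. A margin is therefore needed.

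**The case against.** **The premise is from outside.** No section says that white counts are chronically raised in these patients. That stands: the documents support only a conditional statement, and every count above is illustrative.

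**A reader might infer that such patients can never resolve.** The text does not support that. Two consecutive counts at or below the cut-off suffice, and step 2 shows that ordinary variation can supply them when the usual count is only slightly above it. Nor is 34% to 79% the share left unresolved; it is an upper reading of it.

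**A reader might infer that the pain outcome has the same fault.** It shares the asymmetry, but the outcome is by name an absolute level of severity, for which a fixed threshold is a legitimate choice. Scores are taken in hospital under individualized analgesia (section 3.2), so a usual score of 4 or more does not show that two lower scores are out of reach.

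**A reader might infer that the duration simply copies length of stay.** Section 3.3 assigns no value to an unresolved case, and the schedule stops at Day 7, so longer stays would not be copied. The missing rule for unresolved cases affects the other resolution-based durations too and is a separate gap.

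**The stakes are limited.** This is one of six secondary outcomes, no comparative test is planned, and hydroxyurea use is recorded, so an imbalance in it would be visible. That lowers the priority. It does not remove the problem, because supplying effect and variance estimates is a stated aim.

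**Conclusion.** The point holds for leukocytosis, in conditional form: if a patient's usual count is well above the cut-off, the rule as written will probably keep that patient unresolved after recovery, and the planned data cannot identify who this was. At 1.3 times the cut-off, the chance of meeting the rule within 7 daily counts is at most about 8% under the assumed day-to-day variation. The number affected is unknown. About 4.5 to 14.5 of 20 follows only from the assumed steady-state distribution, the assumed variation and independent daily counts. The change is worth making before enrollment because it is cheap and follows a principle already in section 3.3. For pain, the fixed threshold is defensible.

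**What to change.** In section 3.3, after correcting the unit:

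- At enrollment, before outcomes are known, record the most recent documented steady-state white count from the clinic record, with its date.
- Where it exceeds the cut-off, define leukocytosis as a count above that baseline by a prespecified margin for day-to-day variation, and resolution as two consecutive counts within that margin.
- Report the number per arm using the baseline rule, and show the fixed cut-off result alongside. To allow this, let the fixed cut-off continue to decide when daily counts stop. The baseline rule is met no later than the fixed one, so no blood draws are added.
- Keep the VAS threshold as the pain definition. Recording the usual pain score, to describe patients whose usual score is 4 or more, is optional.

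The cost is one data field and a few sentences. The downsides are that patients without a documented steady-state count keep the fixed cut-off, and that two definitions are mixed in a small sample. This change does not settle what duration to record for a patient still unresolved at discharge or study completion; that needs its own rule.

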3.2 Study Design

This is a single-center, randomized controlled, open-label, pilot study to determine the feasibility of performing a larger multicenter phase III trial to assess the effects of UFH in ACS. Adult patients with SCD (HbSS, SC, or Sβ⁰) aged 18 years or older admitted to UPMC (Presbyterian, Montefiore, Magee, Shadyside) hospitals with a diagnosis of ACS will be eligible for screening to participate in the trial. Subjects meeting inclusion and exclusion criteria and consenting to study will be randomized within 24 hours of diagnosis to one of two treatment arms, Arm A, anticoagulation and standard of care, or Arm B, no anticoagulation and standard of care. Weight-adjusted UFH will be given at doses of 80 units per kilogram followed by 18 units per kilogram per hour intravenously for 7 days, or until discharge, if discharge is shorter than 7 days. UFH will be monitored by standard protocol to maintain the anti-Xa UFH level in the therapeutic range per institutional guidelines.¹⁵ During the study period, if therapeutic anticoagulation is indicated for non-research purposes, it will be given at the discretion of the treating physician.

Standard of care, per the treating physician, will include the following:

- Intravenous fluids, preferably hypotonic saline, will be given to maintain adequate hydration. The specific rate, subsequent changes in rate, and duration will be per the treating physician's discretion.
- Antibiotics will be given to treat pathogens that are responsible for community acquired pneumonia, such as "atypicals" or, if necessary, to provide a broader spectrum of coverage against antimicrobial organisms as the treating physician sees fit.
- Supplemental oxygen will be provided to maintain the arterial oxygen saturation, as recorded by pulse oximetry, greater than or equal to 90%.
- Incentive spirometry will be provided with recommendations to take 10 breaths every 2 hours while awake.
- Pain management will consist of acetaminophen, nonsteroidal antiinflammatory drugs (NSAIDs), or opioids as needed to maintain adequate analgesia. Specifics regarding pain management will be individualized according to each patient's established plan of care as dictated by his or her outpatient hematologist.
- Red blood cell transfusions will be given routinely as standard clinical practice in acute chest syndrome with the goal of preventing progression to acute respiratory failure.

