Further data collected will include information regarding standard of care therapy (collected daily during duration of study), demographics (collected following study enrollment and screening), and medical information (collected following study enrollment and screening). Regarding standard of care therapy, data collected will consist of whether or not intravenous fluids were given; whether or not antibiotics were administered, number of antibiotics received, and class of antibiotics given (penicillin, cephalosporin, macrolide, fluoroquinolone, vancomycin, other); whether or not supplemental oxygen was received with documentation of need for noninvasive positive pressure ventilation or mechanical ventilation; whether or not pain medication was provided, including type of pain medication (opioid, NSAIDs, acetaminophen, other); number of red blood cell transfusions given; and whether or not exchange transfusion was necessary. Demographics include age, race, and sex. SCD related medical information includes number of previous episodes of ACS, current administration of outpatient hydroxyurea, and prior DVT or PE. General medical information includes history of myocardial infarction; chronic lung disease, defined as a documented baseline arterial oxygen saturation less than 90% and/or home supplemental oxygen requirement; previous stroke; and current or former smoker.

Prespecified feasibility criteria are as follows: the ability to enroll potential study participants, which includes the timely notification of hospitalized patients with ACS, the capacity to consent eligible individuals, and the ability to appropriately randomize screened patients within 24 hours of diagnosis, all of which should occur at a frequency greater than or equal to 80%; inclusion and exclusion criteria that does not exclude potential study participants at a frequency greater than or equal to 20%; the proper administration of the study drug at a frequency greater than or equal to 90%; and the ability to completely and accurately collect clinical data of interest at frequency greater than or equal to 90%. The final aim of our pilot study is to provide preliminary data, with respect to treatment effect and variance, for future sample size calculations given the lack of existing data to help guide this process.

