
Potential adverse events include heparin-associated risks, such as allergic reaction, major bleeding, minor bleeding, thrombocytopenia, and heparin induced thrombocytopenia (HIT), or any other adverse reaction suspected secondary to drug administration. All subjects enrolled in the study and received any UFH will be included in the safety evaluation.

A member of the research staff will collect the study data. All data required by the study protocol will be documented in the inpatient electronic medical record system. De-identified subject information will be written on Case Report Forms (CRFs) and all data collected will be stored in locked files at the Hemophilia Center of Western Pennsylvania (HCWP). Additionally, data will be entered into research electronic capture (REDCap) and compared to ensure consistency. No personal identifiers will be associated with the data. The Institutional Review Board (IRB) may inspect records at any time.

A sample size of 20 subjects for the pilot study is based on clinical rather than statistical considerations and should provide a preliminary estimate of primary and secondary clinical outcomes and assess prespecified feasibility criteria as detailed above. Based on 75,000 to 100,000 African Americans with SCD in the United States who develop ACS at a frequency of 8.8 per 100 patient years, with 50% developing ACS at some point during his or her lifetime, and given the fact that approximately 30 patients are admitted annually at UPMC hospitals (Presbyterian, Montefiore, Magee, Shadyside) with ACS, we estimate that at least 80%, or 24 patients per year, will meet inclusion and exclusion criteria, and expect to enroll 10 patients, or slightly less than 50% per year, which should meet the n=20 subjects required for the pilot study.^{3,4} This is a pilot feasibility study, so comparisons will be descriptive, including frequencies and percentages for categorical variables and mean, median, range, and standard deviation for continuous variables.

Demographics and medical information will be summarized with descriptive statistics as well. Adverse events will be summarized by frequency, relatedness, and severity.

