Subjects will be considered enrolled in the study after informed consent is obtained. Each study participant will receive a unique subject identification number. Afterwards, screening assessment will be completed by a member of the research staff. All individuals will have any reason for study exclusion documented. Following enrollment and screening, patients will undergo randomization. Prior to beginning the study, an independent statistician will perform a 1:1 randomization using randomization software ensuring 10 patients are placed in each arm of the study. A card will be labeled heparin or standard of care, placed in a sealed envelope numbered 1 to 20, and stored in locked files at HCWP. Following enrollment and screening, a member of the research staff will access the appropriate numbered envelope to ascertain patient assignment.

Study participants will be free to withdraw at any time by notifying a member of the research staff. Any data collected prior to the time of withdrawal will continue to be used, but no additional information will be collected. Processed blood sample results will continue to be used; however, remaining samples will be destroyed or used as indicated by the subject. The reason and date of study withdrawal for all subjects will be recorded.

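### Total opioid dose is a raw sum with no reference to usual opioid dose, which is not collected; with 10 per arm, chance imbalance could distort the arm difference and add variance to the SD carried forward

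*Combined protocol and SAP*

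**What the plan says.** Total opioid dose is one of six secondary clinical outcomes in Section 3.3, in a list that ends with "duration of moderate to severe pain, total dose of opioids, and the number of red blood cell transfusions administered". Its definition is: "Total dose of opioids will be defined as beginning with randomization, ending with study completion, and measured in milligrams of oral morphine equivalents". Nothing in that definition refers to what the patient takes outside hospital.

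Section 3.2 says analgesics are given as needed to keep pain controlled, with the specifics individualized to each patient's "established plan of care as dictated by his or her outpatient hematologist".

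The baseline items are enumerated: "SCD related medical information includes number of previous episodes of ACS, current administration of outpatient hydroxyurea, and prior DVT or PE". The general medical items that follow are myocardial infarction, chronic lung disease, stroke and smoking. Table 1 footnote 3 repeats the same list. Neither contains an opioid item. The daily standard-of-care record covers "whether or not pain medication was provided, including type of pain medication (opioid, NSAIDs, acetaminophen, other"), which concerns the study period only.

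On allocation, Section 4.2 says "an independent statistician will perform a 1:1 randomization using randomization software ensuring 10 patients are placed in each arm of the study"; no stratification factor is described. Section 4.3 does not exclude chronic opioid users. On analysis, Section 3.3 says "comparisons will be descriptive, including frequencies and percentages for categorical variables and mean, median, range, and standard deviation for continuous variables". The same section gives as the pilot's final aim preliminary data on treatment effect and variance for sizing a later trial.

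**The concern.** The protocol itself names a source of between-patient variation in opioid dose that is set before admission and is unrelated to heparin. The outcome takes no account of it, the allocation does not balance it, and the planned data do not record it. Two patients with the same pain course but different usual regimens could have different totals.

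Two deliverables are exposed. The observed arm difference could owe part of its size, or its direction, to how usual opioid users happened to fall between arms, and a reader of the results would have no baseline table entry with which to judge that. The SD of the raw total also includes whatever variation comes from usual regimens, part of which a baseline covariate could remove. The absence of a hypothesis test does not settle the matter, because the effect and the SD are themselves what the pilot is meant to hand on.

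**Working it through.** **The plan's own figure.** "A sample size of 20 subjects for the pilot study is based on clinical rather than statistical considerations", so no formula reproduces 20. The accrual arithmetic behind it is consistent: 30 × 0.80 = 24 eligible a year; 10/24 = 41.7%, which fits the plan's description of slightly under half; 20/10 = 2 years. The documents give no opioid dose, SD, prevalence of chronic use or correlation. Those inputs below are assumptions, shown over ranges.

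**Step 1. Chance imbalance in a continuous baseline variable.** With 10 per arm, the SD of the difference in arm means is sqrt(2/10) = 0.447 baseline SDs. The chance that the means differ by more than 0.5 SD is 2 × P(Z > 0.5/0.447) = 2 × P(Z > 1.118) ≈ 26%. This assumes approximate normality and holds for any baseline variable; it is not specific to opioids.

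**Step 2. Chance imbalance in the number of usual opioid users.** If K of the 20 are users (assumed), the number in one arm is hypergeometric.

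| K | Arms differ by 2 or more users | Arms differ by 4 or more users |
|---|---|---|
| 4 | 0.58 | 0.09 |
| 6 | 0.63 | 0.14 |
| 8 | 0.65 | 0.17 |
| 10 | 0.66 | 0.18 |

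**Step 3. Leverage of one patient.** Suppose a home dose of h mg/day is carried on in full and simply adds to acute dosing for all 7 days of Table 1 (assumed; earlier discharge would shorten this). One patient then adds 7h mg to the arm total, and 7h/10 = 0.7h mg to the arm mean: 70 mg at h = 100, 210 mg at h = 300. With no SD or typical total in the documents, the importance of these shifts cannot be judged.

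**Step 4. Share of variance due to usual use.** Let q be the proportion of users and D the gap in mean total dose between users and non-users, in within-group SDs. The share is q(1−q)D² / [q(1−q)D² + 1].

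| q | D = 0.5 | D = 1 | D = 2 | D = 3 |
|---|---|---|---|---|
| 0.3 | 5% | 17% | 46% | 65% |
| 0.5 | 6% | 20% | 50% | 69% |

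The share passes one half only when D exceeds 1/sqrt(q(1−q)): 2.5 at q = 0.2, 2.2 at q = 0.3, 2.0 at q = 0.5.

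**Step 5. What adjustment would gain.** With correlation r between usual dose and total dose, residual variance is 1 − r². To show the scale, take a later trial sized on this outcome with a 0.5 SD effect, two-sided 0.05 and 80% power: n per arm = 2(1.960 + 0.842)²(1 − r²)/0.5², rounded up.

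| r (assumed) | Variance removed | n per arm |
|---|---|---|
| 0 | 0% | 63 |
| 0.3 | 9% | 58 |
| 0.5 | 25% | 48 |
| 0.8 | 64% | 23 |

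**Step 6. How well 20 patients would estimate r.** For an observed r of 0.5, Fisher's z is 0.549 with standard error 1/sqrt(17) = 0.243. The limits are 0.549 ± 1.96 × 0.243, or 0.074 to 1.025, which back-transform to r of about 0.07 to 0.77. The variance reduction is then anywhere from about 0.5% to 60%.

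**The case against.** The strongest reply is that this is one of six secondary outcomes in a feasibility pilot whose primary clinical outcome is duration of hospitalization. Comparisons are descriptive, randomization leaves the contrast unbiased on average, and nothing says the later trial will be sized on opioid dose. The raw SD is also the correct input if that trial analyses the raw total. All of this stands, and it limits the priority.

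A reader might go further than the documents allow in three ways.

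- *That the outcome mainly reflects who takes chronic opioids.* No prevalence, dose or correlation is given. Step 4 shows that this needs a gap of about two or more within-group SDs; at a gap of one SD the share is 17% to 20% for q of 0.3 to 0.5.
- *That in-hospital dose is largely fixed by the home regimen.* Section 3.2 also says analgesics are given as needed, which implies titration to pain. A plan of care is not the same thing as a home daily dose.
- *That adjustment would be impossible later.* Section 4.4 keeps a linkage key between study identifier and name, so chart review might recover the dose. What is true is that the plan does not provide for collecting it.

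The contrast with hypoxemia, which Section 3.3 redefines against the patient's own baseline, gives only modest support. That rule covers patients whose baseline already falls below the saturation threshold or who already need oxygen; it is not a covariate adjustment. Fever, leukocytosis and pain have no personal baseline either.

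What survives is that a plausible prognostic variable, pointed to by the protocol's own text, is neither recorded nor described by arm.

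**Conclusion.** The point holds as one of precision and interpretability, not of bias. The definition of the outcome, the omission from both baseline lists, and the unstratified, unadjusted comparison can all be read directly from the documents. The 26% follows from 10 per arm and approximate normality alone. How much usual opioid use would actually distort the difference or widen the SD depends on a correlation that the documents do not give; over the assumed range of 0.3 to 0.8, the removable variance runs from 9% to 64%. Because the outcome is secondary and descriptive, this is a cheap improvement of low to moderate priority, not a defect that threatens the pilot.

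**What to change.** Add one item to the medical information in Section 3.3 and Table 1 footnote 3: pre-admission daily opioid dose in oral morphine equivalents, abstracted from the medication list, with zero and unknown kept distinct. Summarize it by arm.

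Keep the raw total as defined. Beside it, report a supplementary estimate from a linear model with arm and pre-admission dose. Give the raw SD, the adjusted (residual) SD, and the observed correlation with its confidence interval.

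State that the adjusted SD will be used for later sizing only if the later trial prespecifies the same adjustment, and that the imprecision of the correlation will be allowed for. In the illustration above, sizing at 48 per arm on an observed r of 0.5 would fall short if the true r were 0.07, where 62.8 × (1 − 0.07²) = 62.5, so 63 per arm, would be needed.

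The cost is one chart field per patient, one of 18 residual degrees of freedom in the supplementary model, and the risk that the medication list is incomplete or differs from what the patient takes. Patient care and the raw outcome do not change.
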